4 STUDY DESIGN

4.1 Overall Design

This is a randomized, evaluator-blind (dermatologist and ophthalmologist), 2-arm, parallel-group, single-center, non-comparative clinical 'in-use' study to determine the local cutaneous and ocular tolerance of a developmental cosmetic facial serum formulation in healthy female subjects aged 18 to 65 years (inclusive) with clinically evaluated sensitive skin, as determined by a positive response to a LAST, with minimal signs or symptoms of cutaneous irritation and no signs or symptoms of ocular irritation. A reference product, proven to be suitable for use in a sensitive skin population is included to enable the study to be conducted in a randomized and blinded manner, rather than as a single-arm or open-label study, to minimize bias and ensure a robust outcome.

A sufficient number of subjects will be screened (approximately 180) to randomize 90 subjects to ensure that at least 60 subjects (30 per arm) complete the study.

At Visit 1 (screening), subjects who agree to participate in the study by signing the informed consent will be assessed by a qualified dermatologist for baseline clinical assessments of the signs and symptoms of cutaneous irritation and by a qualified ophthalmologist for baseline clinical assessments of the signs and symptoms of ocular irritation. Following these assessments, a LAST will be conducted in the nasolabial region to confirm whether the subject has sensitive skin. Subjects will only be considered eligible to continue in the study if they present a positive response to the LAST. Medical history, Fitzpatrick skin type assessment, prior, current and concomitant medication will also be recorded at this visit. Subjects will be asked to self-assess baseline signs and symptoms of cutaneous and ocular irritation prior to the LAST and any product application.

Subjects will only be considered eligible to continue in the study if they have a dermatologist signs and symptoms cutaneous irritation score of greater than or equal to 0.5 (very slight) for erythema and a score of greater than or equal to 0.5 (very slight) for dryness, a score of 0 (none) or 0.5 (very slight) for scaling and 0 (none) or 0.5 (very slight) for edema. Any subject with a score of 3 (severe) in any cutaneous irritation attribute will exclude the subject from the study, as this does not reflect the target population for the product. Any ophthalmologist signs and symptoms attribute score of greater than 0 (none) will exclude the subject from the study.

For subjects who continue to be eligible to participate in the study, the first application of their assigned product will be at the investigational site, under the supervision of a trained technician.

Subjects will be asked to answer further self-assessment questions of the signs and symptoms of cutaneous and ocular irritation they are experiencing, 1-2 hours after first application. Subjects will then be instructed to apply their assigned product at home again the same evening and twice-daily for 21 (+2) days as part of their normal skin care routine. A paper diary will be provided to each subject to record the number of daily applications of product, from first application at site to final application at home. The final application of product will be at home on the morning of the final visit (Visit 2).

At Visit 2 (final visit), the dermatologist and ophthalmologist will conduct final clinical assessments of the signs and symptoms of cutaneous and ocular irritation, respectively. Subjects will also be asked to conduct a final self-assessment of the signs and symptoms of cutaneous and ocular irritation. Subjects will return their completed diary and supplied product and will subsequently be discharged from the study.

4.2 Rationale for Study Design

Acceptability 'in use' studies aim to determine the irritation potential of topical products in the target population under the intended conditions of use, prior to commercialization.

The investigational product being evaluated is a developmental formulation intended to be used as a cosmetic facial serum by adult consumers with sensitive facial skin. The formulation has been designed to provide topical moisturization while minimizing the quantity of known irritants and allergens. A reference product, proven to be suitable for use in a sensitive skin population is included to enable the study to be conducted in a randomized and blinded manner, rather than as a single-arm or open-label study, to minimize bias and ensure a robust outcome.

Subjects will only be considered eligible to continue in the study if they have a dermatologist signs and symptoms cutaneous irritation score of greater than or to equal 0.5 (very slight) for erythema and a score of greater than or equal to 0.5 (very slight) for dryness, as this is representative of the target consumer for the finished product. Subjects presenting a score greater than 0.5 (very mild) for edema and scaling are excluded from the study as they do not represent the target population for the product.

Any subject with a score of 3 (severe) in any cutaneous irritation attribute will exclude the subject from the study, as this does not reflect the target population for the product.

Per ANVISA guidelines, acceptability studies are indicated to be conducted for a 3-week period of use, taking into account the normal conditions of use.

No formal statistical comparison between the reference product and investigational product is required in order to evaluate the local tolerance of the investigational product.

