5.2 Inclusion Criteria

An individual must meet all of the following inclusion criteria to be eligible for enrollment into the study:

1. Subject provision of a signed and dated informed consent document indicating that the subject has been informed of all pertinent aspects of the study before any assessment is performed.
2. Subject is female who, at the time of screening, is between the ages of 18 and 65 years, inclusive.
3. A subject who is willing and able to comply with scheduled visits, the application schedule, the lifestyle guidelines, and other study procedures.
4. A subject in good general and mental health with, in the opinion of the investigator or medically qualified designee (if the investigator is not suitably qualified), no clinically significant/relevant abnormalities in medical history or upon dermatologist and ophthalmologist examination, or condition, that would impact the subject's safety,

wellbeing or the outcome of the study, if they were to participate in the study, or affect the individual's ability to understand and follow study procedures and requirements.

5. A subject with sensitive facial skin, defined as a positive response to a lactic acid sting test in the nasolabial area.
6. A subject with a dermatologist signs and symptoms of cutaneous irritation score of greater than or equal to 0.5 (very slight) for erythema.
7. A subject with a dermatologist signs and symptoms of cutaneous irritation score of greater than or equal to 0.5 (very slight) for dryness.
8. A subject with a dermatologist signs and symptoms of cutaneous irritation score of 0 (none) or 0.5 (very slight) for scaling.
9. A subject with a dermatologist signs and symptoms of cutaneous irritation score of 0 (none) or 0.5 (very slight) for edema.
10. A subject with an ophthalmologist total signs and symptoms of ocular irritation score of 0 (none).

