8.1.6 Dermatologist Assessment

A qualified dermatologist will visually assess the subject at Visit 1 (baseline) prior to randomization to determine their eligibility to continue in the study. This will ensure the subject is free of any preexisting dermatological pathology prior to using the study products (Edward, 2008). For inclusion into the study each subject should have a dermatologist signs and symptoms cutaneous irritation score of equal to or greater than 0.5 (very slight) for erythema and a score of greater than or equal to 0.5 (very slight) for dryness, a score of 0 (none) or 0.5 (very slight) for scaling and 0 (none) or 0.5 (very slight) for edema. Any attribute score of 3 (severe) will exclude the subject from the study as this is not the intended population for the product.

The intensity of any visual signs of dermal irritation will be recorded according to the grade of the reactions according to the Dermatological Evaluation ([Safety and Other Assessments](#)). The dermatologist is responsible for grading the level of cutaneous irritation and their opinion on the correct classification of the irritation scores is final. Scores will be directly entered into the CRF.

Any observed cutaneous response that can be denoted according to the grade of the reactions will not be considered an adverse event. Only in the case of unusual reactions will these reactions and the consequences observed upon evaluation be documented as AE's.

Any subject with a score of 3 (severe) in any attribute will exclude the subject from the study, as this does not reflect the target population for the product.

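### The Visit 1 dermatologist score both admits the subject and is her baseline; the resulting drift in the primary change has no clear sign, is probably small, and no planned contrast with the reference arm separates it from a product effect

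*Protocol*

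**What the plan says.** Protocol 8.1.6: "A qualified dermatologist will visually assess the subject at Visit 1 (baseline) prior to randomization to determine their eligibility to continue in the study". The Schedule of Activities lists no other dermatologist score before product use, and SAP 3.1 defines baseline as the value before any application. The qualifying score is therefore the baseline.

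Protocol 5.2 sets floors on two attributes. For erythema: "A subject with a dermatologist signs and symptoms of cutaneous irritation score of greater than or equal to 0.5 (very slight) for erythema"; dryness has the same floor. It sets caps on the other two. For scaling: "A subject with a dermatologist signs and symptoms of cutaneous irritation score of 0 (none) or 0.5 (very slight) for scaling"; edema has the same cap. Section 5.3 excludes a score of 3 on any of the four.

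The primary endpoint (Protocol 12.2.6, SAP 4.4.1.1) is the change in the sum of the four attributes. Success (Protocol 3, SAP 4.4.1.1) requires that at least 90% of completed subjects on the investigational product show no one-unit increase.

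The reference arm exists so that the study can be randomised and blinded, "to minimize bias and ensure a robust outcome" (Protocol 4.1). Section 4.2 adds: "No formal statistical comparison between the reference product and investigational product is required in order to evaluate the local tolerance of the investigational product". Protocol 12.2.6 and SAP 4.4.1.2 summarise the change by number and percentage in each arm, without inference. SAP 4.4.1.2 adds a row for changes greater than 1.

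**The concern.** A subject whose reading must clear a floor to get in is more likely to have read high by chance that day, and she tends to read lower next time whatever is applied. A reading that must sit under a cap behaves the opposite way. Change from a qualifying score therefore contains drift unrelated to the product.

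Randomisation gives both arms the same drift in expectation, but it removes the drift only from a contrast between arms. A within-arm percentage held against 90% keeps all of it, and blinding the assessor does not help. Neither document mentions this or says how the reference result should be used when reading the investigational one.

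**Working it through.** **The plan's own figures.** No power, SD or event rate is stated, so there is no power calculation to reproduce. Planned screening yield is 90/180 = 50%. With 30 completers in an arm, 90% means 27 of 30.

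**Direction, attribute by attribute.** Take a reading with mean μ in screened women and visit-to-visit reliability r, on an underlying continuous scale. With no product effect, the expected second reading given the first is μ + r(first − μ). So:

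expected change among those admitted = −(1 − r) × (mean admitted first reading − μ)

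A floor puts the admitted mean above μ, and the change is negative. A cap puts it below μ, and the change is positive. The primary total adds two attributes with floors to two with caps, so its sign depends on how scores are distributed in screened women. The documents do not give that distribution.

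**Size, by simulation with no product effect.** The 0/0.5/1/2/3 scale and all entry rules come from the Protocol. The rest is assumed: reliability 0.5, 0.7 and 0.9, correlation 0.4 between attributes, and four score distributions. The comparison is the entry score as baseline against an independent re-measured baseline in the same subjects. Ranges run over reliability 0.5, 0.7, 0.9.

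| Scenario | Zero on each of erythema, dryness | Scaling / edema above 0.5 | Mean change in total | Rise of at least 1: entry vs re-measured baseline |
|---|---|---|---|---|
| A | 40% | 10% / 2% | −0.17, −0.10, −0.05 | 19.9 vs 25.7%; 18.8 vs 22.2%; 12.9 vs 14.0% |
| B | 20% | 10% / 2% | −0.02, −0.01, −0.01 | 20.6 vs 23.2%; 17.4 vs 18.7%; 10.8 vs 10.9% |
| C | 60% | 5% / 1% | −0.35, −0.22, −0.10 | 15.5 vs 23.9%; 15.6 vs 21.3%; 11.7 vs 13.8% |
| D | 10% | 30% / 15% | +0.25, +0.15, +0.05 | 30.6 vs 26.4%; 24.1 vs 21.4%; 13.6 vs 12.3% |

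Erythema plus dryness fell in every run (−0.03 to −0.44). Scaling plus edema rose in every run (+0.03 to +0.30). With the re-measured baseline the mean change was about 0 throughout, so the drift comes from reusing the entry score.

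**Which scenarios fit the planned yield.** If a share s of screened women meets each floor, both floors are met by between s² (independent attributes) and s (perfect correlation):

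- A, s = 0.6: 36% to 60%, and about 42% at correlation 0.4 (bivariate normal).
- B, s = 0.8: 64% to 80%.
- C, s = 0.4: 16% to 40%, so it cannot reach 50%.
- D, s = 0.9: 81% to 90% before the caps, and about 45% after them.

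A positive lactic acid test and the remaining criteria must also be met. B fits the 50% yield. D falls a little short, A further, and C is ruled out. The entry baseline gives 0.1 to 2.6 points fewer rises in B (for example 23.2 − 20.6 = 2.6) and 1.3 to 4.2 points more in D (30.6 − 26.4 = 4.2). A further simulation restricted to settings near this yield gave mean changes of about −0.11 to +0.24 and mostly 0 to 4 points, in either direction.

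**Effect on the 27-of-30 rule.** P(at least 27 of 30), binomial, at reliability 0.7:

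- B: 0.21 at a true 82.6% without a rise, against 0.16 at 81.3%.
- D: 0.05 at 75.9%, against 0.09 at 78.6%.

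**Precision of a between-arm difference.** Half-width = 1.96 × √(2p(1 − p)/30):

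- p = 5%: 1.96 × √(0.095/30) = 11.0 points.
- p = 10%: 1.96 × √(0.18/30) = 15.2 points.
- p = 20%: 1.96 × √(0.32/30) = 20.2 points.

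**The case against.** The case against acting has four parts.

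- **The design is declared non-comparative.** The question is absolute tolerance against a preset 90% rule, and Protocol 4.2 gives its reason. This stands as a reason for no test and no margin. It does not make the within-arm percentage free of drift.
- **The reference arm is already reported.** Both arms are tabulated on the same endpoint, so a reader can set them side by side. This stands; only the contrast and an instruction to use it are missing.
- **The contrast is imprecise and relative.** A half-width of 11 to 20 points exceeds the drift it would cancel. The reference is a marketed anti-redness serum, so the difference measures tolerance relative to that product and not to no product. Both limits stand and should be stated.
- **Harm to the decision is not shown.** At reliability 0.7 in scenarios B and D, a product with no effect usually misses 27 of 30 under either baseline. These runs do not show an irritating product passing.

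A reader might also infer that scores tend to fall under this design, and that the 90% rule is therefore easier to meet for any product, including an irritating one. The documents do not support this. That inference leaves out the caps, which raise the total and in scenario D make the rule harder to meet. The settings with the largest falls need so many screened women at zero that the planned 50% yield could not be reached.

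**Conclusion.** The structural point holds. A single Visit 1 score is both entry criterion and baseline, the success rule reads one arm, and no planned estimate separates entry-selection drift from a product effect. The sign of the net drift in the total score cannot be determined from the documents. At the planned yield its size is probably a few percentage points or less on the share with a rise of at least 1.

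That size rests on assumed reliability, correlation and score distributions, and on a yield that is only an approximate planning figure. No figure stated in the plan is contradicted. This is a minor, cheap improvement and does not invalidate the design.

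A related mismatch strengthens the case for editing the same table: the success rule turns on an increase of 1, while SAP 4.4.1.2 counts changes greater than 1. Totals move in half-point steps, so a subject who rises by exactly 1 fails the rule but is not counted in that row.

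**What to change.** 1. In SAP 4.4.1.2, tabulate for both products the percentage of subjects without an increase of at least 1 in the total score, replacing the row for changes greater than 1. Use completed subjects as the denominator, so that the table answers the success rule as written.
2. In the same table, give the investigational-minus-reference difference in that percentage with a 95% confidence interval. Label it descriptive, with no test and no margin.
3. In Protocol 4.2, add a sentence such as: because the eligibility score is also the baseline, the within-arm result will be read beside the reference arm.
4. State the limits next to the estimate: a half-width of roughly 11 to 20 points at true rates of 5% to 20% with 30 per arm, and a comparator that is an active marketed serum.

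The cost is one changed row, one added row and one sentence, with no extra subjects or visits. The price is a wide interval and a less simple success statement.

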4.3 Justification for Dose

The first administration will be supervised by a trained technician when the subjects are at the site at for Screening/Visit 1.

Subjects will be instructed to use the product twice-daily (morning and evening) as part of their normal facial care regimen, post cleansing and prior to moisturization (if appropriate), in their usual manner. The instructions for use provided to subjects in this study are consistent with those intended to be communicated to consumer when the product is made freely available for purchase: "Apply twice daily to freshly cleansed skin in place of your current serum and before your moisturizer".

Subjects who already use a facial serum will be instructed to replace their current serum with the product they have been assigned to use for the duration of the study.

4.4 End of Study Definition

A subject will be considered to have completed the study if they complete all phases of the study, including the last visit or the last scheduled procedure shown in the Schedule of Activities. The end of this study is defined as the date of the last subject's last visit.

5 STUDY POPULATION

5.1 Type and Planned Number of Subjects

Healthy female subjects, aged 18 to 65 years with clinically assessed sensitive skin and no ophthalmological conditions will be enrolled into this study. Female subjects with sensitive skin have been selected as they are the target consumers for the finished product with greater familiarization and habitual use of facial products.

A sufficient number of subjects will be screened (approximately 180) to randomize 90 subjects to ensure that at least 60 subjects (30 per arm) complete the study. It is deemed that 30 subjects per arm are considered sufficient to assess the primary endpoint: dermatologist assessment of signs and symptoms of cutaneous irritation total score. The sample size for this study has been selected based on clinical considerations and to ensure compliance with the ANVISA Guideline for the Safety Evaluation of Cosmetic Products (ANVISA, 2012) which mandates an investigational product be tested on at least 30 subjects

This study can fulfill its objectives only if appropriate subjects are enrolled. The following eligibility criteria are designed to select subjects for whom participation in the study is considered appropriate. All relevant medical and non-medical conditions should be taken into consideration when deciding whether a subject is suitable for this protocol.

Subject eligibility to participate in the clinical study should be reviewed and documented by an appropriate member of the investigator's study team before subjects are included in the study.

Site personnel performing the subject inclusion and exclusion criteria and subject eligibility should be the investigator, a suitable Medically Qualified Person (MQP) or designee as appropriate. This should be documented in the site logs.

5.2 Inclusion Criteria

An individual must meet all of the following inclusion criteria to be eligible for enrollment into the study:

1. Subject provision of a signed and dated informed consent document indicating that the subject has been informed of all pertinent aspects of the study before any assessment is performed.
2. Subject is female who, at the time of screening, is between the ages of 18 and 65 years, inclusive.
3. A subject who is willing and able to comply with scheduled visits, the application schedule, the lifestyle guidelines, and other study procedures.
4. A subject in good general and mental health with, in the opinion of the investigator or medically qualified designee (if the investigator is not suitably qualified), no clinically significant/relevant abnormalities in medical history or upon dermatologist and ophthalmologist examination, or condition, that would impact the subject's safety,

wellbeing or the outcome of the study, if they were to participate in the study, or affect the individual's ability to understand and follow study procedures and requirements.

5. A subject with sensitive facial skin, defined as a positive response to a lactic acid sting test in the nasolabial area.
6. A subject with a dermatologist signs and symptoms of cutaneous irritation score of greater than or equal to 0.5 (very slight) for erythema.
7. A subject with a dermatologist signs and symptoms of cutaneous irritation score of greater than or equal to 0.5 (very slight) for dryness.
8. A subject with a dermatologist signs and symptoms of cutaneous irritation score of 0 (none) or 0.5 (very slight) for scaling.
9. A subject with a dermatologist signs and symptoms of cutaneous irritation score of 0 (none) or 0.5 (very slight) for edema.
10. A subject with an ophthalmologist total signs and symptoms of ocular irritation score of 0 (none).

5.3 Exclusion Criteria

An individual who meets any of the following exclusion criteria will not be eligible for enrollment into the study:

1. A subject who is an employee of the investigational site, either directly involved in the conduct of the study or a member of their immediate family; or an employee of the investigational site otherwise supervised by the investigator; or, a GSK CH employee directly involved in the conduct of the study or a member of their immediate family.
2. A subject who has participated in other studies (including non-medicinal studies) involving investigational product(s) within 30 days prior to study entry and/or during study participation.
3. A subject with, in the opinion of the investigator or medically qualified designee, an acute or chronic medical or psychiatric condition that may increase the risk associated with study participation or investigational product administration or may interfere with the interpretation of study results and, in the judgment of the investigator or medically qualified designee, would make the subject inappropriate for entry into this study.
4. A subject who is pregnant (self-reported).
5. A subject who is breastfeeding.
6. A subject with known or suspected intolerance or hypersensitivity to the study materials (or closely related compounds) or any of their stated ingredients.
7. A subject who, in the opinion of the investigator or medically qualified designee, should not participate in the study.
8. A subject unwilling or unable to comply with the [Lifestyle Considerations](#) required by this study, as described in this protocol.
9. A subject with current or recent (within last 6 months before the start of the study) history of atopic lesions and/or eczema
10. A subject with a history of allergic reactions to topical-use products, cosmetics or medications or their ingredients.

11. A subject with any history of significant diseases or medical conditions known to alter skin or eye appearance or physiologic response (e.g. diabetes) which could, in the opinion of the Investigator, preclude topical application of the investigational products and/or interfere with the evaluation of the test site reaction.
12. A subject presenting open sores, pimples, or cysts at the application site (face).
13. A subject with an active dermatosis (local or disseminated) that might interfere with the results of the study.
14. A subject with a dermatologist signs and symptoms of cutaneous irritation score of 3 (severe) for erythema, edema, scaling or dryness.
15. A subject considered immune-compromised.
16. A subject currently using any medication which in the opinion of the investigator, may affect the evaluation of the investigational product, or place the subject at undue risk
17. A subject who has used any of the following topical or systemic medications up to two weeks before the screening visit: immuno-suppressants, antihistamines, non-steroidal anti-inflammatory drugs (NSAIDS), and/or corticosteroids.
18. A subject who has used oral or topical treatment with vitamin A acid and/or its derivatives up to 1 month before the screening visit.
19. A subject who has been vaccinated up to 1 month before the screening visit or who are intending to receive a vaccination during their participation in the study.
20. A subject with a recent history (within the last 5 years) of alcohol or other substance abuse.
21. A subject with any skin marks on the face that might interfere with the evaluation of possible skin reactions (e.g. pigmentation disorders, vascular malformations, scars, tattoos, excessive hair, numerous freckles).
22. Subjects with corneal ulcers, keratoconus, blepharitis, meibomitis, pterygium, chemosis, moderately or severe hyperemia or other active ocular diseases.
23. A subject who has previously been enrolled in this study.

